Morphine administration for acute pain after mastectomy surgery has many side effects. Regional block techniques as paravertebral block and thoracic epidural anaesthesia has possible complications and technical difficulties.

The new alternative regional techniques such as erector spinae plane block and serratus anterior plane block are clinical trials for providing a safe, easy and painless anesthetic procedure with good hemodynamic and recovery profile with adequate perioperative analgesia for a large section of patients undergoing mastectomy operation in order to reduce opioids consumption and subsequently avoid opioid-related adverse effects.

Research question

Is there difference between the Ultrasound-Guided Erector Spinae Plane Block and the Serratus anterior plane Block in providing peri operative analgesia for patients undergoing Modified Radical Mastectomy?

Hypothesis

Null hypothesis (H₀):

There is no difference between Ultrasound-Guided Erector Spinae Plane Block and Serratus anterior plane Block in providing peri operative analgesia for patients undergoing Modified Radical Mastectomy under general anesthesia.

Alternative hypothesis (H₁):

There is difference between Ultrasound-Guided Erector Spinae Plane Block and Serratus anterior plane Block in providing peri operative analgesia for patients undergoing Modified Radical Mastectomy under genera anesthesia.

Aim of the work

To compare between Ultrasound-Guided Erector Spinae Plane Block and Serratus anterior plane Block for peri operative analgesia in patients undergoing Modified Radical Mastectomy operations under general anesthesia.

Objectives

To:

- Assess sensory block (onset, quality and duration) of both erector spinae plane block and serratus anterior plane block and detect which of them gives better analgesia.
- Assess post operative static and dynamic pain.
- Assess the time of first analgesic requirement post Modified Radical Mastectomy surgery.
- Detect the presence of side effects with general anesthesia.
- Assess patient satisfactions.

Patients And Methods

1- Technical design:

- **Site of the study:**

The study will be conducted in operating room in Zagazig University Hospitals.

- **Duration of the study:**

The study will be conducted over two years.

- **Sample size:**

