- All participating patients will be interviewed preoperatively during their preoperative preparation. The goal and endpoints of the study

will be discussed. Understanding of the block will be reviewed and emphasized, informed consent will be taken.

- On physical examination, special attention will be given to document vital signs, cardiac, chest condition and exclude contraindications.
- All patients will be investigated by complete blood count, Liver functions test, kidney functions test and coagulation profile.

Steps of Performance:

- *Preparation:*
 - All patients will be kept fasting for minimum 6 hours before the operation.
 - All patients will be clinically examined in the preoperative period and routine investigations will be checked and at the same time, whole procedure will be explained. Ten centimeters visual analog scale (VAS) (**Metwally et al., 2016**), (0 – no pain and 10 – worst pain imaginable) will be also explained during preoperative visit.
 - The monitors attached included non-invasive blood pressure (NIBP), electrocardiography (ECG), and pulse oximetry.
 - An 18 G I.V cannula will be secured in the opposite hand and fluid will be started. supplemental oxygen will be administered at 6 to 8 L/min via face mask. Procedural sedation will be provided intravenously by midazolam 0.03 to 0.04 mg/kg, as needed

- **Technique:**

- **Erector Spinae Plane Block:**

Position

sitting position

Type of needle

Using 22 gauge spinal needle 10 cm length.

Scanning

Linear ultrasound probe is placed in a longitudinal parasagittal orientation 3 cm lateral to the T5 spinous process.

The erector spinae muscle is identified superficial to the tip of The T5 transverse process.

Needle insertion

The needle is inserted in- plane superior to inferior approach. The tip of the needle is placed into the fascial plane on the deep aspect of erector spinae muscle.

The location of the needle tip is confirmed by visible normal saline fluid spread separating erector spinae muscle off the bony shadow of the transverse process on ultrasonographic imaging .

Local anesthetic and volume

Injection of 20 ml of bupivacaine 0.25 %. (Singh et al., 2019)

II. Serratus Anterior Plane Block:

Position

The patient lies supine with placing the ipsi-lateral upper limb in abduction at 90° position.

Type of needle

Using 22 gauge spinal needle 10 cm length.

Scanning

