After skin sterilization, Ultrasound device with high frequency [9-12] and superficial linear probe that is first placed inferior to the middle of the clavicle and moved laterally and downward to locate the 1st rib where pectoralis major and pectoralis minor muscles are identified at this US window.

The US probe is moved toward axilla till serratus anterior muscle is identified above 2nd, 3rd and 4th ribs. The transducer is held at a slightly oblique angle at the level of the 4th and 5th rib, with the upper edge supero-anterior and the lower edge infero-anterior.

Needle insertion

After infiltration of the skin at puncture site with 3 ml of lidocaine 1%, the needle is inserted inplane between the anterior serratus and the latissimus dorsi muscle on the mid-axillary line.

Local anesthetic and volume

Injection of 20 mL of 0.25% bupivacaine. (**Khemka et al., 2019**)

Assessment of block:

Onset time of sensory block

Time between injection of the drugs and loss of pin prick sensation in operating field, pin prick test done with sterile 25G needle.

Quality of sensory block will be graded as :

- Grade 0 : normal sensation
- Grade 1: loss of sensation to pinprick.
- Grade 2: loss of sensation to light touch (**Swami et al., 2012**).

Duration of sensory block

Time between onset of sensory block to the first report of postoperative pain at the surgical site that is **VAS score >3**, with first analgesic requirement by the patient.

The patients will be delivered to the operating room to receive general anesthesia with good monitoring.

General anesthesia:

- It will be standardized for all patients.

- Fentanyl 2 mcg/kg, propofol 2 mg/kg will be intravenously administered, followed by cisatracurium 0.15 mg/kg to facilitate endotracheal intubation with a suitable size of endotracheal tube.
- Lungs will be ventilated by pressure controlled mode to maintain normocapnia ($\text{PaCO}_2 = 35\text{-}45 \text{ mmHg}$) and isoflurane/O₂ mixture will be administered.
- Concentration of the inhalational agent will be 1.2 MAC of isoflurane, Heart rate and mean arterial blood pressure will be recorded every 10 minutes.
- Incremental doses of fentanyl can be given in inadequate analgesia {presented by tachycardia and hypertension (mean arterial blood pressure) $>20\%$ from baseline} after exclusion of other causes}, total amount of fentanyl consumption intraoperative will be calculated.
- Paracetamol 15ml/kg will be administered by iv infusion to all patients.

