- After completion of the surgery, inhalational anesthesia will be stopped and the patient will receive neostigmine (0.05 mg/kg) and atropine sulphate (0.01 mg/kg).

Postoperative:

- After recovery from anesthesia, the patient will be transferred to the post-anesthesia care unit.
- All patients will receive paracetamol as standard intravenous infusion analgesia at dose of 15mg/Kg every 8 hours (maximum dose: 4 g / day).
- Pain will be observed and recorded using the pain assessment on a 0-10 cm line [visual analogue scale (VAS) (**Metwally et al., 2016**); 0=no pain, 1 to 3 = mild pain, 4 to 6 = moderate pain, 7 to 10 = severe pain].

- The pain is measured both at rest and movement (arm movement of 90° and sitting from lying down position) after explanation of the procedure to the patient at 2,4,8,12,18 & 24 hours after surgery by an observer blinded to treatment groups.
- All patients will be assessed for the time to first rescue analgesic and when the patient suffer from pain at score equal or above 3 on VAS, the patient will receive morphine (dose: 0.1 mg/kg intravenous as initial dose then 0.025 to 0.05 mg/kg every 5 minutes till the pain is relieved not exceeding 4 mg/h). Total morphine consumption will be calculated.
- Post-operative nausea and vomiting will be noticed, recorded using a categorical scoring system (0 = none, 1 = mild, 2 = moderate, 3 = severe) and treated, Ondansetron 4 mg IV will be administered in case of reported nausea and/or vomiting.
- Patient satisfaction will be assessed post operatively using satisfaction score (4= excellent, 3 = good, 2 = fair and 1 = poor) (**Ross et al., 2009**).

Complications and side effects:

It may include failure of the block, intra-muscular hematoma, pleural perforation, Post-operative nausea and vomiting (PONV), sedation and respiratory depression. These complications will be observed and recorded.

Data collection:

From each patient the following data will be collected upon admission:

1-Demographic data:

- Name
- Age
- Body Mass Index
- Hospital diagnosis
- Date of admission in hospital
- Medical and past history

- ASA grade I-II
- Type of operation : unilateral mastectomy surgery
- Duration of operation

2-Sensory block assessment: onset, quality of sensory block, duration of the block.

3-Hemodynamics (HR, Mean Arterial Bl.Pr), total intra-operative fentanyl consumption.

4-Static and dynamic pain scores (VAS) at 2, 4, 8, 12, 18 and 24 hours post-operatively.

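### Block duration ends at a VAS strictly above 3, but rescue morphine is due at 3 or above, so a block patient first rescued at exactly 3 has no settled block end

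*Protocol*

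**What the plan says.** The Protocol uses the VAS to trigger two different things.

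- **End of the block.** Under *Assessment of block*, the duration of sensory block starts at block onset. It stops at the first postoperative pain report at the surgical site with a VAS strictly above 3, "with first analgesic requirement by the patient".
- **Rescue treatment.** Under *Postoperative*, "when the patient suffer from pain at score equal or above 3 on VAS, the patient will receive morphine". The threshold here includes 3.

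The scale is introduced in *Preparation* as a ten-centimetre VAS and described again under *Postoperative* as a "pain assessment on a 0-10 cm line", with the bands "1 to 3 = mild pain, 4 to 6 = moderate pain, 7 to 10 = severe pain". Pain is scored "at 2,4,8,12,18 & 24 hours after surgery by an observer blinded to treatment groups".

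Block duration is a declared outcome. The first item under *Objectives* is "Assess sensory block (onset, quality and duration) of both erector spinae plane block and serratus anterior plane block", and item 2 of *Data collection* lists "onset, quality of sensory block, duration of the block". Time to first rescue is collected separately, as item 5.

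**The concern.** The block-end definition treats two events as simultaneous: pain above 3 and the first need for an analgesic. The rescue rule can separate them. A patient who reports exactly 3 must be given morphine, so her first analgesic has been given, yet her pain has not passed the level that ends the block. No other text reconciles the two rules.

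Both rules operate at the bedside while data are being collected, so this is not an analysis detail that could be left to a statistical analysis plan. Two people recording the same patient could enter different durations, or one could enter a value and the other leave it blank. If recorders wait for a score above 3, the interval includes time under morphine, and the variable no longer measures the block alone.

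**Working it through.** **The two rules side by side**

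| VAS at first pain report | Rescue morphine due (3 or above)? | Pain condition for block end met (above 3)? |
|---|---|---|
| Below 3 | No | No |
| Exactly 3 | Yes | No |
| Above 3 | Yes | Yes |

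The rules agree everywhere except at exactly 3.

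**Readings for a block patient first rescued at exactly 3**

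1. Both conditions must hold at the same event. They did not at the first rescue, and no later analgesic can be the first. Block duration has no end point.
2. The VAS condition governs. The block ends at the first later score above 3, after morphine has been given.
3. The first analgesic requirement governs. The block ends at rescue, although the score did not exceed 3.

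Reading 2 sets aside the first-requirement condition and reading 3 sets aside the strict threshold. Reading 1 keeps both but yields no value.

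**Size per affected patient, reading 2 minus reading 3**

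Inputs: scheduled scores at 2, 4, 8, 12, 18 and 24 h (*Postoperative*) and 25 patients per arm (*Sample size*).

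Assumption: she is rescued at a scheduled assessment between 2 and 18 h, and pain above 3 is first recorded at the next one.

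Formula: difference = (next time − rescue time) × 60 min; shift in the arm mean = difference / 25.

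| Rescued at | Next score | Difference | Shift in mean of 25 |
|---|---|---|---|
| 2 h | 4 h | 2 × 60 = 120 min | 120/25 = 4.8 min |
| 4 h | 8 h | 4 × 60 = 240 min | 240/25 = 9.6 min |
| 8 h | 12 h | 4 × 60 = 240 min | 240/25 = 9.6 min |
| 12 h | 18 h | 6 × 60 = 360 min | 360/25 = 14.4 min |
| 18 h | 24 h | 6 × 60 = 360 min | 360/25 = 14.4 min |

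A report above 3 between assessments would make the difference smaller. A first score above 3 at a later assessment would make it larger, so 360 min is not an upper limit. If she is rescued at 24 h, or never again scores above 3, reading 2 gives no end point either. With no affected patients the difference is 0.

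**How often it could arise**

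The Protocol gives no figure for this. Read continuously, a 10 cm line would seldom give exactly 3. Whole-number scoring would make 3 an ordinary value, and indeed the lowest score that triggers rescue. The pain bands leave no place for a value such as 3.5 and so would fit whole numbers, but the Protocol does not state the scoring resolution.

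**The case against.** The strongest reply is that the text already points to reading 3. The definition is tied to the first analgesic requirement, and the rescue rule fixes when that arises. On this view reading 2 is the weakest, because a later score above 3 in a patient already given morphine does not come with her first requirement. The minute figures then describe one scenario under a poor reading. This has some force: reading 3 is a sensible intention to attribute to the authors. But it can be adopted only by disregarding the stated threshold, just as reading 2 disregards the other condition. The text does not settle the choice, and reading 1 remains open as the literal one.

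The figures are indeed a scenario. Morphine is titrated until pain is relieved, so the next score above 3 may come several assessments later or never. They show scale, not expected impact.

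Two further points stand in full. The number of patients affected may be zero. And because first-rescue time is recorded in its own right, reading 3 could be applied afterwards to every affected patient whose block onset was recorded. That limits the damage, but a declared outcome should not depend on a choice of definition made after the data are in.

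**Conclusion.** The inconsistency is real and follows directly from the wording of the two rules. Its reach is narrow: block duration only, in the two block arms only, and only in patients first rescued at exactly 3. How many that would be cannot be derived from the Protocol.

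Reading 2 can only give a longer duration than reading 3. One affected patient moves the mean of an arm of 25 by 4.8 to 14.4 min if pain above 3 is first recorded at the next scheduled assessment; the shift is smaller with an earlier report and larger with a later one. No direction of bias between the arms is claimed. Time to first analgesia, the basis of the sample size, keeps a usable definition. Severity is minor, and confidence that the two rules conflict is high.

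**What to change.** Use the same VAS threshold in the block-duration definition (*Assessment of block*) and in the rescue rule (*Postoperative*). Whether it is 3 or above, or strictly above 3, is the investigators' clinical choice. Add that the block is taken to end no later than the time of first rescue morphine, which keeps opioid effect out of block duration at any threshold.

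The cost is at most one sentence in each of the two sections. The times needed are already collected; no extra patients or visits and no change in sample size are required.

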Assuming that the mean \pm standard deviation of time of first analgesia requirement in erector spinae block group is 416 ± 108.2 minute and that in serratus anterior block is 343 ± 99.7 minute (Eldemrdaش et al., 2019), so sample size is calculated by open EPI programme to be 75 cases (25 cases in each group) with confidence level of 95% and power of test 80%.

Inclusion criteria:

- Written informed consent from the patient.
- Age: 21 – 60 years old.
- Gender: female patients.

- Body mass index: < 35 kg/m².
- Physical status: ASA grade I-II (American society of anesthesiologists).
- Type of operation: unilateral modified radical mastectomy operation.

Exclusion criteria:

- Patient with known history of allergy to study drugs.
- Chronic use of analgesics or drug dependence.
- Patients not able to understand pain assessment test.
- Anatomical abnormalities.
- Neuropathic disease.
- Pregnancy or breast feeding.
- Other contraindication of regional anesthesia e.g. septic focus at site of injection.
- patient with coagulopathy or on anticoagulant therapy.

- **Tools of data collection :**
 - Anesthetic sheet to all patients.
 - Intra operative assessment of vital signs by the anesthesiologist.
 - Post-operative assessment of pain, use of systemic analgesics and patient satisfaction in ward.

2- Operational design:

- **Type of the study:** prospective comparative randomized controlled clinical study.
- **Randomization:**

A computer-generated table will be used to divide patients equally into 3 study groups.

- **Group C (Control group) (n=25)** patients will receive only general anesthesia for Modified Radical Mastectomy.
- **Group E (n=25)** patients will receive Ultrasound-Guided Erector Spinae Plane Block before induction of general anesthesia for Modified Radical Mastectomy.
- **Group S (n=25)** patients will receive Ultrasound-Guided Serratus anterior Block before induction of general anesthesia for Modified Radical Mastectomy.

- **Equipment needed for technique:**
 - High frequency linear transducer ultrasound.
 - 22 gauge spinal needle 10 cm length.
 - Local anesthetic: bupivacaine 0.25% (for the erector spinae plane block and serratus plane block) and lidocaine 1% (for local infiltration at the site of injection).
 - Sterile preparation for the site of needle insertion, equipments and anesthesiologist.

All Cases Will Undergo:

The process

- **Patient Examination:**

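### Nausea and vomiting, sedation and respiratory depression are not tied to the timed, blinded visits, so their ascertainment is unstandardised and not stated to be blinded

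*Protocol*

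**What the plan says.** **Purpose.** The Rationale presents the two blocks as a route to good analgesia "in order to reduce opioids consumption and subsequently avoid opioid-related adverse effects". The Objectives include detecting side effects.

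**Named events.** Protocol, Complications and side effects, lists block failure, haematoma and pleural perforation together with "Post-operative nausea and vomiting (PONV), sedation and respiratory depression". The method given for the whole list is "These complications will be observed and recorded".

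**PONV.** The Postoperative section adds: "Post-operative nausea and vomiting will be noticed, recorded using a categorical scoring system", running from 0 (none) to 3 (severe). Treatment follows symptoms: "Ondansetron 4 mg IV will be administered in case of reported nausea and/or vomiting". No assessment time, recall window or assessor is given.

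**Timed visits.** The same section has pain at rest and on movement measured "at 2,4,8,12,18 & 24 hours after surgery by an observer blinded to treatment groups". The times and the blinding are attached to pain.

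**Data lists.** Tools of data collection describes the ward tool as "Post-operative assessment of pain, use of systemic analgesics and patient satisfaction in ward". The Data collection section opens with "From each patient the following data will be collected upon admission". It fixes times for the pain scores (item 4) and a 24-hour window for morphine (item 6). Complications (item 7) carry neither.

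**The concern.** Opioid side effects are part of the argument for the blocks, so readers of the results will compare them between arms. For that comparison to mean something, each patient needs the same chance of having an event found, by the same definition, from someone unaware of the arm. Pain is set up this way. PONV, sedation and respiratory depression are not.

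Without a scale or cut-off, what counts as sedation or respiratory depression depends on who is looking. Without fixed times, it depends on when they look. Without stated blinding, and with a control arm that receives general anaesthesia alone, the person noting the event may know the arm.

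A statistical analysis plan cannot repair this. What is measured, when and by whom has to be settled before the first patient is treated; a respiratory rate or sedation level that was never written down cannot be recovered later.

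**Working it through.** The plan gives no figure on this point, so the check is mainly a comparison of its own provisions.

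**1. Provisions side by side** (Postoperative; Complications and side effects; Data collection)

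| Outcome | Scale or definition | Stated times | Stated blinded assessor |
|---|---|---|---|
| Pain at rest and on movement | 0-10 cm VAS with severity bands | 2, 4, 8, 12, 18, 24 h | Yes |
| PONV | 0-3 score | None | No |
| Sedation | None | None | No |
| Respiratory depression | None | None | No |

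Pain is therefore stated to be recorded at 6 of 6 visits. The three side effects are not stated to be recorded at any of them, which is not the same as saying that nothing else is recorded there.

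**2. Is a relevant measurement fixed elsewhere?** Pulse oximetry appears under Preparation, before the block and anaesthesia. Tools of data collection places vital signs intra-operatively. Item 3 of Data collection covers heart rate, mean arterial pressure and intra-operative fentanyl. No postoperative respiratory rate, oxygen saturation or sedation score is stated.

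**3. Could detection differ by arm?** Under Randomization, Group C (n=25) has no block and no sham, and blinding is stated only for the pain observer. Rescue morphine is titrated at 5-minute intervals, so a rescued patient probably has more bedside contact. Both features make unequal detection possible. Neither shows that it occurs.

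**4. What unequal detection would do.** The document gives no event rates or detection probabilities, so every value here except n = 25 is an assumption.

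Expected recorded events per arm = 25 × true risk × detection probability. With equal true risk, the recorded risk ratio (block/control) = detection in block ÷ detection in control.

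| True risk, both arms | Detection control / block | Recorded events control / block | Ratio |
|---|---|---|---|
| 20% | 90% / 60% | 25×0.20×0.90 = 4.5; 25×0.20×0.60 = 3.0 | 0.67 |
| 40% | 90% / 60% | 9.0; 6.0 | 0.67 |
| 20% | 80% / 50% | 4.0; 2.5 | 0.63 |
| 20% | equal (100% / 100%) | 5.0; 5.0 | 1.0 |
| 20% | 60% / 90% | 3.0; 4.5 | 1.5 |

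The ratio depends wholly on the assumed detection. The last two rows show that no bias, or bias in the other direction, follows just as readily from other assumptions.

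**The case against.** **Complications are planned data.** They are to be observed and recorded, and they stand on the list collected from each patient. The PONV score has a zero category, so it can be completed for a patient without symptoms. This stands. A reader might infer that events would be found only by chance; the text does not support that.

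**The ward tool list is not exclusive.** Nothing in it says that other assessments are ruled out, and the Postoperative section itself adds a PONV score and complications. This stands too. The list cannot be read as limiting ward assessment to pain, analgesics and satisfaction.

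**The direction of bias is not shown.** A reader might infer that events will be found more often where more morphine is given, and so more often in the control arm. That is plausible, but it rests on an inference from the titration interval. More recorded events with more morphine could also be a true drug effect, and the present recording could not separate the two.

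**All arms share some contact.** Every patient passes through the post-anaesthesia care unit and is seen at the six pain visits. This weakens any picture of patients left unobserved for 24 hours, but it does not supply a sedation or respiratory record.

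**The comparison is secondary.** The hypotheses concern analgesia, the sample size rests on time to first analgesic, and the side-effect objective is worded descriptively. This limits the weight of the point. It does not remove it, because the Rationale relies on avoiding opioid side effects.

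**Conclusion.** The point holds in a limited form. The protocol gives PONV an untimed score, gives sedation and respiratory depression no measure at all, and does not extend the timed, blinded assessment to any of the three. Ascertainment is unstandardised and not stated to be blinded, in a trial whose control arm has no sham. Events may be missed and detection may differ between arms.

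The size and direction of any resulting bias cannot be established from the document; the recorded ratios of 0.63 to 1.5 above only reflect the detection probabilities assumed. The pain and time-to-first-analgesic comparisons are not affected. This is a cheap improvement to a stated secondary objective, and it has to be made in the protocol before data are collected.

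**What to change.** In the Postoperative section, state that at each existing visit (2, 4, 8, 12, 18 and 24 h) the same blinded observer records four items for every patient, whether or not morphine was given:

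- the 0-3 PONV score;
- a fixed, named sedation score;
- respiratory rate;
- SpO2.

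Define the sedation and respiratory depression events in advance on these scheduled values. Base the between-group comparison on them, over the same 24 hours as morphine consumption. List events noted between visits separately, so that contact prompted by rescue does not feed into the comparison. Add the times to item 7 of Data collection. This concerns recording only and alters no treatment rule.

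**Cost.** One protocol sentence and four fields on the visit sheet, with no extra visits or staff. That is 4 × 6 = 24 values per patient, or 24 × 75 = 1,800 in all. At an assumed minute per visit, it adds about 6 minutes per patient.

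**Downside.** More mild events will be recorded. Visits are 2 to 6 hours apart, so brief events between them may still be missed.
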